Effect of nasal positive airway pressure versus standard care on oxygenation and ventilation during propofol- based sedation for colonoscopy in patients with high risk of airway obstruction: a prospective randomized controlled trial.

NCT05524220

Version Date: 01/27/2023

Effect of nasal positive airway pressure versus standard care on oxygenation and ventilation during propofol-based sedation for colonoscopy in patients with high risk of airway obstruction: a prospective randomized controlled trial.

Principal Investigator: [name]

Co-PIs: [name]

[name]

[name]

[name].

Statistician: [name], M.S.

Contacts:

[name]., VP, Medical Director
Vyaire Medical
[REDACTED]
[REDACTED]

SUMMARY TABLE

Title	Effect of nasal positive airway pressure versus standard care on oxygenation and ventilation during propofol-based sedation for colonoscopy in male and female patients with high risk of airway obstruction: a prospective randomized controlled trial.
Project Office	
Study Size (# of patients)	150 patients
Study Design	Prospective randomized controlled single site trial.
Primary Outcome	Elapsed time from initiation of induction to the first airway intervention.
Secondary Outcome	
 1. Compare the amount of propofol administered during induction and total dose administered for procedure 2. Compare Modified Observer's Assessment of Alertness/Sedation Scale (MOAAS) scores immediately prior to endoscopic intubation and during the procedure 3. Compare the length of time from induction to endoscopic insertion 4. Compare the incidence and duration of procedural interruptions (ie: number of times and length of time the endoscope is removed from the patient) 5. Compare the incidence, duration, and reason for airway maneuvers 6. Compare the length of time for the procedure (ie: length of time from procedure start to procedure end) 7. Compare recovery times 
 a. Ready to discharge b. Actual discharge 8. Compare patient satisfaction scores (visual analog scale (VAS)) immediately after procedure 
 a. Overall experience b. Quality of sedation c. Pain experienced during procedure d. Pain after the procedure e. Nausea after awakening f. Vomiting after awakening g. Dizziness after awakening h. Recollection of scope insertion i. Recollection of scope removal j. Awake during the procedure 9. Compare patient tolerance to SuperNO₂VA™EtCO₂ compared to control (ie: face mask at 10LPM) 10. Compare anesthesiologists satisfaction scores 
 a. Overall experience b. Rating of sedation c. Difficulty of patient to sedate 11. Compare the incidence of cardiac complications
Inclusion Criteria	
 1. Age 18 years of age or older 2. All Patients undergoing colonoscopy (male and Female) 3. American Society of Anesthesiology (ASA) Physical Status I-III 4. BMI $\geq 30 \text{ kg/m}^2$ or documented Obstructive Sleep Apnea

	5. Has provided written informed consent
Exclusion criteria	
 1. Inpatient status 2. Active Congestive Heart Failure Exacerbation 3. Untreated ischemic heart disease 4. Acute exacerbation of respiratory disorders, including COPD and asthma 5. Emergent procedures 6. Pregnancy 7. Previous enrollment in this study 8. Inability to provide informed consent 9. Additional medical testing planned for the same day 10. History of allergic reaction to Propofol 11. Tracheostomy 12. Supra-glottic or sub-glottic tumor 13. Gastrointestinal tract obstruction or delayed transit (including delayed gastric emptying, gastric bezoar, achalasia, toxic megacolon). 14. Prisoners 15. Unable to fit SuperNoVa
Study Procedures	
Pretreatment Evaluation	Candidates will be assessed if the SuperNova fit is difficult or impossible
On-Study Visits	N/A
Follow-up Visits	N/A
End of Study Visit	Subjects will be assessed in PACU before he or she is discharged
Brief Analysis Plan	
Based on the literature, the elapsed time from anesthesia induction to the first airway intervention was 19 ± 10 min in the Mask group ($n=63$) vs. 10 ± 12 min in the Control group ($n=73$, $P < 0.001$)¹⁵. For sample size calculation we used the standard sample size calculation equation¹⁶:
 $n = \frac{2(Z_{\alpha} + Z_{1-\beta})^2 \sigma^2}{\Delta^2}$ 
σ = variation of the measurement Δ = difference to be detected
 
σ and Δ are based on the outcome values from previous publication.¹⁵ This publication showed a time difference (Δ) of 9 minutes with a standard deviation (σ) of ± 10 minutes in both intervention groups. To be able to detect an even smaller time difference of 5 minutes and with a standard deviation of 10 minutes and a drop of percentage of 20% ($\alpha = 0,05$ and $1-\beta = 0,80$) we calculated $n_1=n_2= 75$. A total of 150 patients will be enrolled.

1. OBJECTIVES

Primary Objective

The primary objective of the study is to prospectively and randomly compare elapsed time from initiation of induction to the first airway intervention in patients considered high risk for hypoxia (ie: BMI ≥ 35 kg/m² and/or documented Obstructive Sleep Apnea).

Endpoints of Interest

1. Compare the amount of propofol administered during induction and total dose administered for procedure
2. Compare Modified Observer's Assessment of Alertness/Sedation Scale (MOAAS) scores immediately prior to endoscopic intubation and during the procedure
3. Compare the length of time from induction to endoscopic insertion
4. Compare the incidence and duration of procedural interruptions (ie: number of times and length of time the endoscope is removed from the patient)
5. Compare the incidence, duration, and reason for airway maneuvers
6. Compare the length of time for the procedure (ie: length of time from procedure start to procedure end)
7. Compare recovery times
8. Compare patient satisfaction scores (visual analog scale (VAS)) immediately after procedure
9. Compare patient tolerance to SuperNO₂VA EtCO₂ compared to control (ie: face mask at 10LPM)
10. Compare endoscopist satisfaction scores for
11. Compare anesthesiologists satisfaction scores
12. Compare the incidence of cardiac complications

Study Design

This is a prospective randomized controlled single site trial.

2. BACKGROUND

Colonoscopy is a common procedure performed in the U.S. Most patients undergoing endoscopy require sedation to have an acceptable experience.¹⁻² It is a necessity because the ability to interpret images and perform therapeutic or diagnostic procedures are dependent on the subjects cooperation. Reliable imaging cannot be obtained if the patient is not cooperative. Propofol is a commonly used sedative that has been used in several studies for endoscopic procedures and is associated with low complication rates in healthy patients (ie: ASA I and III).³⁻⁵ However, recent prospective studies have shown that hypoxemia frequently occurs during endoscopic procedures in patients with a BMI > 30 kg/m² or have a history of OSA⁶⁻⁹ and the mortality rate for sedation in the endoscopy suite is significantly higher than that of the comparable cases performed in operating room.¹⁰ Although the cause of the high mortality in GI suite has yet to be determined, it seems to be related to hypoxia and/or hypercarbia due to respiratory depression and upper airway obstruction from sedation.¹⁰

Continuous positive airway pressure (CPAP), applied nasally or via facemask, has been shown to be more effective at minimizing hypoxia than other devices under sedation or general anesthesia.¹¹⁻¹² However, it requires a special mask and CPAP machine with high-fresh gas flows which may not be routinely equipped in GI endoscopy suites due to space and cost constraints.¹³ Therefore, a simplified CPAP system could be a surrogate for a conventional CPAP machine for procedures requiring sedation or general anesthesia with spontaneous breathing via a natural airway. Recently, a simple, novel CPAP device was developed, which

includes a sealed nasal mask and disposable, flow-inflating hyperinflation bag (SuperNO₂VA Et™ Satellite Set, Revolutionary Medical Devices, USA).¹⁴ A small pilot study by Ghebremichael, et al. demonstrated safety and efficacy with the use of the SuperNO₂VA Et™ device for nasal mask ventilation (NMV) in anesthetized and paralyzed patients.¹⁴ It is also demonstrated that this device reduces the incidence and severity of hypoxia under sedation during colonoscopy.¹⁵ The objectives of our study are 1) to compare oxygenation and ventilation spontaneously ventilating obese patients or those with diagnosed or undiagnosed OSA undergoing day colonoscopy under propofol based sedation in between the SuperNO₂VA Et™ nasal positive airway pressure (PAP) device and routine care with face mask for O₂ supply and 2) to determine its capacity to monitor expired CO₂.

2. DISCUSSION OF SUBJECT POPULATION

2.1. Subject Characteristics

The study population for this investigation is all adults who have a BMI ≥ 30 kg/m² and/or documented OSA scheduled to receive Propofol based sedation for colonoscopy.

2.2. Inclusion and Exclusion Criteria

a) Inclusion Criteria:

1. Age 18 years of age or older
2. Patients undergoing lower endoscopy procedure (may be upper and lower)
3. American Society of Anesthesiology (ASA) Physical Status I-III
4. BMI ≥ 30 kg/m² and/or documented Obstructive Sleep Apnea
5. Has provided written informed consent

b) Exclusion Criteria:

1. Inpatient status
2. Active Congestive Heart Failure Exacerbation
3. Untreated ischemic heart disease
4. Acute exacerbation of respiratory disorders, including COPD and asthma
5. Emergent procedures
6. Pregnancy
7. Previous enrollment in this study
8. Inability to provide informed consent
9. Additional medical testing planned for the same day
10. History of allergic reaction to Propofol
11. Tracheostomy
12. Supra-glottic or sub-glottic tumor
13. Gastrointestinal tract obstruction or delayed transit (including delayed gastric emptying, gastric bezoar, achalasia, toxic megacolon).
14. Prisoners

2.3. Discussion of Subject Population:

Patients with either a BMI ≥ 30 kg/m² and/or a documented Obstructive Sleep Apnea scheduled for colonoscopy with Propofol sedation are at increased risk for severe hypoxemia intra-operatively and post-operatively. In addition patients with OSA usually fall into three scenarios. Those that are diagnosed with OSA and are using their CPAP, those that are diagnosed with OSA but do not use CPAP, and the undiagnosed OSA patient. Therefore, this patient population is at higher risk for respiratory depression and hypoxia and the associated morbidity.

3. SUBJECT IDENTIFICATION, RECRUITMENT AND CONSENT**3.1. Method Of Subject Identification And Recruitment**

Subject consenting will take place at the LBJ medical center prior to the procedure by key research personnel such as PI, Co-PIs, and/or study coordinators. Subject initials and/or study identification number will refer to the subjects.

3.2. Consent Process

Subjects deemed eligible to participate in the study will be explained in detail the purpose, nature and procedures of the study, as well as the potential risks, benefits and alternatives. They will be given a consent form to read and if they so choose, to discuss with friends, family, and other clinicians. They will be invited to ask questions and, after all questions are answered to their satisfaction, invited to sign the consent form. The key research personnel (with proper delegation of authority) will participate in the consenting process to ensure the subject has full understanding of the procedure and risks. No study-specific procedure will be performed before the consent form is signed.

Subject participation in this investigation is voluntary. Written informed consent is required from all subjects prior to the subject's participation in the investigation. Also, an obtained permission of the faculty anesthesiologist, in charge of the patient's anesthesia care, must also be granted for subject participation. If the subject is illiterate or unable to adequately read the informed consent form, a witness' signature and a cross mark or a fingerprint of the subject is required. In accordance with FDA regulation 21 CFR Part 50, informed Consent shall be obtained prior to any study procedure. The original of the signed consent will be retained at the investigational site. A signed copy of the consent will be given to the subject. While not anticipated, Sponsor will report any failure to obtain subject consent to the IRB within 5 days of learning of such an event, as required by regulation.

Prior to participating in this investigation, the site will be required to have an IRB-approved Informed Consent Document. Any modifications to the consent must be approved by Sponsor and by the IRB of record. The Principal Investigator is responsible for obtaining and maintaining the approved informed consent and forwarding an IRB-stamped copy to Sponsor.

3.3. Costs to the Subject

None

3.4. Payment for Participation

A total of \$30 will be paid to each subject for the index participation of this study.

3.5. Return of Individual Research Results

Not Applicable.

4. METHODS AND STUDY PROCEDURES

5.1 Instruments

The SuperNO₂VA™EtCO₂ (Nasal Oxygenating Ventilating Apparatus) mask is indicated to deliver gas, create a seal, and provide positive pressure while placed over a patient's nose and connected to either an anesthesia circuit or hyperinflation bag during respiratory, anesthesia, and resuscitation procedures. The SuperNO₂VA™EtCO₂ mask is also intended to facilitate simultaneous oxygenation and ventilation during intubation, as the mask covers only the patient's nose, leaving the clinician with an unobstructed view of the airway.

5.2 Methods:

This study involves the oxygenation, continuous positive airway pressure, and ventilation of a subject via nasal mask and oxygenation via a closed facemask. The interventions directly related to this study are that of supplement oxygen, and continuous nasal CPAP intra-operatively

Patients will be randomized in groups of ten to one of two groups using a random number table. Group A: Standard care with a facemask. Group B: SuperNO₂VA™EtCO₂.

For each anesthetic case, a preoperative history and physical and intraoperative record will be documented (table 1).

Table 1: General Patient characteristics	
Age (years)	
Gender (M/F)	
Height (cm)	
Weight (kg)	
BMI (kg/m ²)	
ASA classification (I-III)	
Diagnosed OSA on home CPAP	
Diagnosed OSA not on home CPAP	
STOP-BANG Score	
Patient Co-morbidities*	

*Co-morbidities include any history of: hypertension, diabetes, coronary disease, valvular disease, arrhythmia, cerebrovascular disease, active cancer, tobacco use, pulmonary disease, renal disease, liver disease.

Once in the endoscopy suite, the patients will have continuous monitoring of heart rate, end tidal CO₂ (EtCO₂), O₂ saturation, and non-invasive blood pressure monitoring with an interval no longer than 5 minutes. Patients randomized to group A, the anesthesia provider will supply oxygen via facemask at 10LPM. Patients randomized to group B, the anesthesia provider will attach the SuperNO₂VA™ EtCO₂ circuit port to the hyperinflation bag with the oxygen flow rate to 10 L/min. Initial dosing bolus 0.5-1.0 mg/kg actual body weight of Propofol will be administered for sedation and MOAA/S scores will be assessed. Nursing or the research assistant will then record the patient's MOAA/S score. If the patient's MOAA/S score is ≥ 4 , additional 10-20mg boluses will be administered every 30 – 90 seconds until a MOAA/S score of <4 reached. Once a MOAA/S score of < 4 is reached the endoscopist will perform endoscopic intubation and the goal will be to maintain a MOAA/S score of <4 until the procedure is over. If the patient's MOAA/S score ≥ 4 , additional 10 – 40mg bolus of propofol will be administered every 30 – 90 seconds until a MOAA/S score of <4 is reached. Once a MOAA/S score of < 4 is reached the endoscopist will perform endoscopic intubation and the goal will be to maintain a MOAA/S score of <4 until the procedure is over.

90 seconds until the MOAA/S is <4. The measurements that will be made are the following: Elapsed time from initiation of induction to the first disappearance of expired CO₂ on capnography, the incidence, severity, and time of oxygen desaturation, number of airway maneuvers performed, duration of airway maneuvers, reason for performing the airway maneuver, the onset time of administration of sedation, the duration of the procedure, the total dosage of the medication, vital signs - blood pressure, heart rate, and oxygen saturation, the time to full recovery, and patient cooperation. Nursing or the research assistant will document their patient's depth of sedation, cooperation with procedure, and safety. Patients will recover in the endoscopy suite. The patients will have continuous monitoring of heart rate, O₂ saturation, and BP monitoring and MOAAS Score. The time to discharge will be obtained for each patient. Patients will also complete a satisfaction and pain questionnaire before they are discharged. A statistician using student T-test, Fishers exact test, and other statistical methods they deem appropriate will analyze the collected data.

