9. CONFIDENTIALITY OF DATA AND INFORMATION STORAGE

All study participants will be assigned a study number. The PI will maintain the key to the study number and medical record number in a password locked UTH computer. Information about study subjects will be kept confidential and managed according to the requirements of the Health Insurance Portability and Accountability Act of 1996 (HIPAA). Patient data will be entered into a password protected electronic spreadsheet and online database (i.e. REDCap). Only the investigators, who have been invited to participate in the study and who are registered with the IRB, as well as have documented completion of all IRB and HIPAA regulations will have access to patient data, but not the medical record key.

Electronic records will be stored for 5 years after study conclusion on the institution's password protected computer, after which time they will be deleted. If there is a breach in confidentiality or violation of IRB and HIPAA regulations, the IRB will be notified in a timely manner (within 7 days) and appropriate actions taken thereafter. All data used in the analysis and reporting of this investigation will be de-identified.

In order to ensure compliance with the Health Insurance Portability and Accountability Act (HIPAA), all subjects enrolled in the study will be required to provide authorization to disclose Protected Health Information (PHI). This authorization will be included in the informed consent document as required by the IRB. In all study reports and in any resulting publications, subjects will not be referred to by their initials and/or study identification number.

The co-PIs will monitor for safety. Data safety will be ensured by having all patient consents and information stored in the REDCaps system. After randomization patient and study data outside the REDCaps system will only be identified by study number. Any recruitment data and randomization tables will be stored as a single copy in a locked cabinet in a PI's secured Faculty office.

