4.1. Randomization

A random number generator program will be used to assign sequential qualified study cases to control group (N = 69) or SuperNO₂VA™EtCO₂ group (N = 69) before collection of additional demographic information and before anesthetic and surgical care. After study group assignment, baseline data will be collected, including age, gender, height, weight, and BMI.

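### Randomisation is described in two ways with two different arm sizes, and no allocation concealment is stated beyond a locked cabinet in a PI's office

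*Combined protocol and SAP*

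**What the plan says.** **Generation.** Section 5.2 (Methods): "Patients will be randomized in groups of ten to one of two groups using a random number table". Section 4.1 (Randomization, placed after section 10.1): "A random number generator program will be used to assign sequential qualified study cases to control group (N = 69"), with the same number in the device group. Section 4.1 mentions no blocks or groups.

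**Target.** The Brief Analysis Plan in the summary table and section 10.1 both give 75 per arm, 150 in total.

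**Custody.** Section 9 (Confidentiality): "randomization tables will be stored as a single copy in a locked cabinet in a PI's secured Faculty office".

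**Recruitment.** Under section 3.1, consent is taken "by key research personnel such as PI, Co-PIs, and/or study coordinators". Section 3.2 adds that "an obtained permission of the faculty anesthesiologist, in charge of the patient's anesthesia care, must also be granted".

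**Visibility.** In section 5.2 the anesthesia provider sets up the assigned device. For the control arm: "Patients randomized to group A, the anesthesia provider will supply oxygen via facemask at 10LPM". The other arm wears the nasal device joined to a hyperinflation bag, so the two look different. No blinding is described.

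**Concealment.** No section describes sealed envelopes, central or web assignment, an independent list holder, or who releases each assignment. REDCap is named in section 9 only as a data store.

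**The concern.** There are two problems. First, a statistician asked to build the list cannot tell from the text whether it is blocked, or whether it should hold 138 or 150 assignments.

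Second, the written arrangements do not keep the next assignment from a person who may be recruiting. Several entry decisions involve judgement. The treating anesthesiologist must agree to participation, and the summary table excludes patients whom the device does not fit, a criterion missing from the list in section 2.2. Foreknowledge could act through either decision.

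The primary outcome, time from induction to the first airway intervention, depends on clinicians who can see the device; section 5.3 counts a chin lift or jaw thrust as a maneuver. If harder airways were steered toward one arm, that selection bias would add to any bias in deciding when to intervene. Section 4.2 adjusts only for characteristics found to differ significantly. The baseline table includes BMI and STOP-BANG but no direct airway examination, so steering on clinical impression could go uncorrected.

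**Working it through.** **1. Where 75 and 69 come from.** Inputs from section 10.1: difference 5 min, SD 10 min, alpha 0.05 (two-sided assumed, as the text does not say), power 0.80, 20% dropout.

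n = 2(1.960 + 0.842)² × 10² / 5² = 62.79 per arm, i.e. 63.

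- 62.79 × 1.2 = 75.3, which matches the stated 75.
- 62.79 × 1.1 = 69.07, which matches 69.

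So 75 follows from the stated 20% allowance, applied as a multiplier. The 69 fits a 10% allowance that the documents do not state. That origin is inferred from the arithmetic.

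**2. Do groups of ten deliver the stated arms?** Assume 5:5 within each ten.

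- 150 / 10 = 15 complete blocks, giving exactly 75/75.
- 138 = 13 complete blocks (65/65) plus 8 patients. Reaching 69/69 needs those 8 to split 4:4, with probability C(8,4) × C(2,1) / C(10,5) = 70 × 2 / 252 = 0.556.
- Under simple unblocked randomisation, 69/69 has probability C(138,69) / 2¹³⁸ = 0.068.

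So 69/69 is possible but not guaranteed under 5:5 blocks of ten, while 75/75 is exact.

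**3. Predictability under 5:5 blocks of ten.** With m = 5 per arm per block:

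- Assignments fixed by the earlier ones (one arm already full): 2m/(m + 1) = 10/6 = 1.67 per block. That is 16.7%, or 25 of 150.
- Correct guesses when always naming the arm that is behind: m + (4^m / C(2m,m) − 1)/2 = 5 + (1024/252 − 1)/2 = 6.53 per block. That is 65.3%, or about 98 of 150, against 50% under simple randomisation.

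Enumeration of all 252 possible blocks gives the same two figures. Both require sight of every earlier assignment. The certain assignments also require the block boundaries; the guess needs only the running count, because complete blocks are balanced.

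For an observer who sees a random half of earlier assignments (an illustrative assumption) but knows the boundaries, simulation gives about 0.5% certain and 57% guessed correctly. Anyone who sees the list knows 100%.

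**4. Would varying the block size help?** The same formula gives expected correct guesses of 2.83 (size 4), 4.10 (size 6), 5.33 (size 8) and 6.53 (size 10). With sizes chosen equally often:

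- 6/8/10: (4.10 + 5.33 + 6.53) / 24 = 66.5%
- 4/6/8: (2.83 + 4.10 + 5.33) / 18 = 68.1%

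Undisclosed varying sizes take away the certain assignments. They do not lower the best-guess rate, and smaller blocks raise it slightly.

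**The case against.** The strongest reply is that much of this is loose drafting. A table and a program may be two names for one step, and section 4.1's silence on blocks is not a denial of them. That is fair, and the difference in method alone would be minor. The conflict that cannot be read away is 69 against 75 per arm.

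A reader might infer that blocks of ten rule out 69/69. They do not, as the 0.556 shows. A reader might also take fixed 5:5 blocks as stated. The text says only groups of ten. The 5:5 reading is the natural one, because giving whole groups of ten to one arm could produce neither 75/75 nor 69/69, but it remains an inference. That the trial is open-label is likewise inferred, from visibly different devices and the absence of any blinding.

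On custody, a reader might conclude that the list holder is the recruiter. The documents do not say so: section 9 refers to an office belonging to a PI, and section 3.1 lists coordinators as an alternative. The overlap is possible and not prevented. The cabinet is locked, but a lock keeps out others, not the office holder.

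The plan also goes part of the way on timing. Section 4.1 assigns qualified cases before anesthetic care, and section 3.2 bars study procedures before consent. However, section 4.1 also collects age, height, weight and BMI after assignment, although age and BMI decide eligibility. The order therefore needs stating outright.

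**Conclusion.** The point holds in two parts. The two randomisation descriptions need to be reconciled, above all 69 per arm (138) against 75 per arm (150). Separately, the plan states no concealment procedure beyond a locked cabinet in the office of a PI, in a trial where PIs may consent patients and the assigned device is visible.

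The 17% certain and 65% guessed are upper limits. They rest on assumed 5:5 blocks and an observer with complete knowledge of earlier assignments and block boundaries; partial knowledge gives much less. Access to the list is the larger weakness, since it reveals everything.

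The documents do not support a claim that allocation has been or will be subverted, and no bias in the primary outcome can be estimated from them. The change should be made before enrolment, because concealment cannot be restored afterwards.

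**What to change.** Use one description in sections 5.2 and 4.1, covering these elements:

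- A computer-generated 1:1 list with 75 per arm, replacing 'N = 69' so that it agrees with section 10.1 and the summary table.
- Preparation and custody by the study statistician or another person who neither recruits nor treats patients.
- Block sizes not disclosed to site staff. Varying them is worthwhile only for removing certain assignments.
- Release of each assignment only after consent and confirmed eligibility. Use REDCap if its randomisation module is available (the documents name REDCap only for data); otherwise use sequentially numbered, opaque, sealed envelopes.
- Removal of the list from the PI's office, with section 9 amended to match.

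The cost is protocol wording and minor set-up work. The planned total of 150 does not change.

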5.3 Definitions of Events

- Airway maneuver: consists of either airway maneuvers such as chin lift, jaw thrust, , mask ventilation, or the insertion of a nasal or oral airway, supraglottic device, or ETT
- Oxygen desaturation: SpO₂ ≤ 90% for ≥ 15 seconds
- Cardiac complications is defined by a change in either SBP or DBP > 25% from baseline, a change in heart rate > 25% from baseline, arrhythmias, and ST-changes on EKG (ST depression or elevation).
- Full recovery is defined as the time from endoscope withdrawal until a MOAA/S score of 5 was achieved and the patient could drink liquids and ambulate independently.
- Full recovery until actual discharge is defined as the interval from full recovery until the patient exited the recovery room.
- Induction to full sedation is the time from initial administration of intravenous sedative or analgesic to the insertion of the endoscope
- Intra-procedural period was defined as the time of first scope insertion until the last scope removal.
- Procedural interruption is defined as the removal of the endoscope due to a respiratory complication
- Modified Observer's Assessment of Alertness/Sedation Scale (MOAAS) from 1 – 5

MOAAS:

- 0 No response after painful trapezius squeeze
- 1 Responds only after painful trapezius squeeze
- 2 Responds only after mild prodding or shaking
- 3 Responds only after name is called loudly and/or repeatedly
- 4 Lethargic response to name spoken in normal tone
- 5 Responds to name spoken in normal tone

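### The primary time to first airway intervention has no rule or suitable named test for patients who need no intervention, and the Section 5.2 measurement list omits that time

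*Combined protocol and SAP*

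**What the plan says.** **Primary outcome.** The summary table gives it as "Elapsed time from initiation of induction to the first airway intervention". Section 1 repeats it, aiming to "compare elapsed time from initiation of induction to the first airway intervention in patients considered high risk for hypoxia". The sample-size text starts from a published result for the same kind of interval: "the elapsed time from anesthesia induction to the first airway intervention was 19 ± 10 min in the Mask group", against 10 ± 12 min in controls.

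**Analysis.** Section 4.2 names no test for the primary outcome as such. It assigns logistic regression to incidence and severity. For durations it assigns a t-test, with a Wilcoxon test as fallback, and it promises both per-protocol and intention-to-treat analyses. Section 5.2 adds that a statistician using the t-test, Fisher's exact test and "other statistical methods they deem appropriate will analyze the collected data".

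**Incidence.** The secondary outcomes include a comparison of the incidence, duration and reason for airway maneuvers.

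**Measurements.** Section 5.2 states: "The measurements that will be made are the following: Elapsed time from initiation of induction to the first disappearance of expired" CO₂. For the airway it lists "number of airway maneuvers performed, duration of airway maneuvers, reason for performing the airway maneuver".

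**Definitions.** Section 5.3 has an entry that begins "Airway maneuver: consists of either airway maneuvers such as chin lift, jaw thrust" and goes on to mask ventilation and airway devices. It has no entry for airway intervention.

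**Population.** The primary objective refers to BMI ≥35 and/or documented sleep apnea. The summary inclusion criteria and Sections 2.1, 2.2 and 2.3 use BMI ≥30.

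**The concern.** Time to a first event is undefined when the event does not happen. A patient who goes through the whole colonoscopy without an airway intervention has the best possible result on this outcome, yet has no number to enter into a t-test. The plan does not say whether that patient is left out, given the procedure length, or treated as censored.

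The choice can change the answer. The device is meant to delay or prevent interventions, so the share without an event may differ between groups because of treatment. Comparing mean times only among patients with an event would then compare two groups that are no longer the randomised ones. If the device mainly spares patients who would have needed help late, its remaining times look short. If it mainly spares those who would have needed help early, they look long. The direction of the bias cannot be known in advance.

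The halfway review of the primary endpoint, and the early-stopping provision in Section 4.2, would inherit the same gap.

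**Working it through.** **1. Does the plan allow for patients without an event?** Yes. If every patient had an airway maneuver, incidence would be 100% in both groups and comparing it would be pointless.

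**2. Can the named tests use such patients?** A t-test needs a number for each patient. A Wilcoxon test needs at least a rank. Neither takes a no-event indicator as it stands. Logistic regression handles the yes/no question but not the time. An intention-to-treat analysis of the time therefore needs a rule, and none is given.

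**3. How many patients could be affected?** The documents give no expected share. As an assumption, for scale only:

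| Assumed share without event | Patients of 150 with no time | Events remaining |
|---|---|---|
| 10% | 0.10 × 150 = 15 | 135 |
| 30% | 0.30 × 150 = 45 | 105 |
| 50% | 0.50 × 150 = 75 | 75 |

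**4. What is the sample size based on?** The inputs are a difference of 5 min, SD 10 min, α = 0.05 (taken as two-sided) and power 0.80. Then n = 2(1.960 + 0.842)² × 10² / 5² = 62.79 per group. Adding 20% gives 62.79 × 1.2 = 75.3, which matches the stated 75 per group. This is a comparison of two means that assumes every analysed patient has a time. The documents do not say how the cited publication treated patients without an intervention.

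**5. What would a log-rank or Cox analysis depend on?** It depends on the number of events D. With equal groups, two-sided α = 0.05 and 80% power, the Schoenfeld formula gives the detectable hazard ratio as exp(−2 × 2.802 / √D):

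- D = 135: exp(−5.603 / 11.619) = 0.62
- D = 75: exp(−5.603 / 8.660) = 0.52

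These figures are before dropout. The documents state no target hazard ratio, so they do not show whether power is adequate. They show only that the two-means calculation would no longer describe the primary test.

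**6. The measurement list set beside the outcomes.**

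| Item | Ends at first airway intervention | Ends at loss of expired CO₂ |
|---|---|---|
| Primary outcome, summary table | yes | no |
| Primary objective, Section 1 | yes | no |
| Secondary outcomes / endpoints of interest | not applicable | not listed |
| Measurement list, Section 5.2 | not listed | yes |

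The only elapsed time from induction in the 5.2 list is for an event that is not a listed outcome. The primary interval is not in that list.

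**The case against.** **A suitable method is not excluded.** Section 5.2 leaves room for other methods, and a rank test can place patients without an event at the most favourable tied rank. Both points are true, and they shape the fix. They do not close the gap, because neither the method nor the ranking rule is stated in advance.

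**The time may well be captured.** Section 5.2 lists the onset time of sedation, which supplies the start, and the duration of each maneuver, which requires noticing when it begins. The list also leaves out other named outcomes, such as procedural interruptions, so it is not exhaustive. The case report form exists but is not shown. This stands: a reader might infer that the primary time will not be recorded, and the documents do not support that.

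**There are not two primary endpoints.** A reader might infer that Section 5.2 sets up a rival primary endpoint. It does not. Both places that name this trial's primary outcome or objective agree, and Section 5.2 never calls the CO₂ interval primary. The Background gives that interval a possible home, either in comparing oxygenation and ventilation or in the aim "to determine its capacity to monitor expired CO₂". The documents do not settle which. What remains is an omission from a list plus a measure with no stated role.

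**The BMI difference is slight.** All eligibility and population text agrees, so there is no real doubt about who can be enrolled.

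**Conclusion.** The main point holds. The primary outcome is undefined for patients without an intervention, the plan itself allows for such patients, and neither the tests named for durations nor any stated rule deals with them. This should be fixed before any look at outcome data, including the halfway review.

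The size is unknown. The range of 15 to 75 patients rests on an assumed 10% to 50% without an event. No loss of power is claimed, and none can be computed, because the documents give neither an event rate nor a hazard ratio. That 4.2's duration tests apply to the primary outcome is a reading: it is an elapsed time, and no other test is assigned to it.

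The omission from Section 5.2 supports the point and is certain on the text, but whether it affects data capture is not. The BMI mismatch is a minor wording matter. Enrolled patients with BMI 30 to below 35 and no documented sleep apnea fall outside the stated objective. A reader might infer that the wrong patients would be enrolled, and the consistent eligibility text does not support that.

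**What to change.** **Section 4.2.** Name one primary analysis that keeps every randomised patient. Two options would serve:

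- a log-rank or Cox analysis, with patients without an event censored at a pre-specified end of observation, for example last scope removal, which Section 5.3 already uses to close the intra-procedural period;
- a rank test in which patients without an event share the most favourable rank, with the rule written down in advance.

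**Data.** Record a no-event indicator for each patient.

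**Section 5.2.** Add the clock time of the first airway intervention. The investigators should confirm whether this means the airway maneuver of Section 5.3, and should state the role of the interval to CO₂ loss.

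**Section 1.** Reconcile the BMI wording of the primary objective with the summary inclusion criteria and Sections 2.1 to 2.3, so that the objective describes the population enrolled.

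**Cost.** The change is small: wording in these sections and, if the case report form lacks them, one time field and one indicator. If log-rank or Cox is chosen, Section 10.1 and the summary table's analysis plan should also say that the 75 per group came from a comparison of means and that power under the new test depends on the number of events. No added patients or procedures are proposed.
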